#### **10.4. Interim Analysis**

No interim analysis will be performed in this study.

#### **10.5. Analysis Populations**

##### **10.5.1. Intent-to-Treat (ITT) Population**

The ITT population is defined as all subjects who were randomized. Efficacy analysis will be performed using the ITT population; subjects will be analyzed as randomized. In addition, ITT population will be used to summarize demographics, and baseline and disease characteristics.

##### **10.5.2. Safety Population**

The safety population includes all subjects who received at least one dose of any one of the three study drugs (ibrutinib, chlorambucil, or obinutuzumab). The safety analysis will be performed using the safety population; and subjects in the safety population will be analyzed as treated.

##### **10.5.3. Pharmacokinetic Evaluable Population**

The PK-evaluable population includes subjects who received at least one dose of ibrutinib and had at least one post-treatment sample obtained.

##### **10.5.4. Additional Analysis Populations**

Additional analysis populations, which might be used for sensitivity analyses and biomarker studies, are defined in the SAP.

#### **10.6. Control for Bias**

The following study design components will facilitate the control for bias:

- Large (approximately 212 subjects)
- Multicenter
- Randomized

The randomization code will be controlled through a centralized procedure and will not be known to Sponsor personnel directly involved with study conduct or data analysis until after the final analysis. The key efficacy endpoints will be determined by the IRC who is independent to

any study procedure and treatment information. The detail information will be described in the study bias control plan.

## **10.7. Efficacy Analyses**

### **10.7.1. Primary Endpoint and Methods**

The primary efficacy endpoint is **Progression-free Survival (PFS)**, which is defined as the time from the date of randomization until confirmed disease progression (assessed by the IRC per IWCLL 2008 criteria, with modification for treatment-related lymphocytosis) or death from any cause, whichever occurs first. Subjects who withdraw from the study or are considered lost to follow-up without prior documentation of disease progression will be censored on the date of the last adequate disease assessment. For subjects without an adequate post-baseline disease assessment, PFS will be censored on the date of randomization. Adequate disease assessment is defined as physical examination and CBC, or CBC and CT scan. The detail of the statistical model and censoring rule will be described in SAP.

The analysis of PFS will be performed in the ITT population to compare PFS (as assessed by the IRC) for the two treatment arms using a log-rank test. Distribution of PFS including median and its corresponding 95% confidence interval (CI) will be summarized for each treatment arm using the Kaplan-Meier estimate. The estimate of the hazard ratio and its corresponding 95% CI will be computed using a Cox proportional hazards model.

### **10.7.2. Secondary Endpoints and Methods**

#### **10.7.2.1. Overall Response Rate**

Overall response rate (ORR) is defined as the proportion of subjects who achieve a CR, CRi, nPR, or PR, over the course of the study as evaluated by the IRC using IWCLL 2008 criteria, with modification for treatment-related lymphocytosis. Subjects who do not have any post-baseline response assessment will be considered as nonresponders. A chi-square test will be used to compare the two treatment arms.

#### **10.7.2.2. Rate of Minimal Residual Disease (MRD)-negative Responses**

A chi-square test will be used to compare the rate of MRD-negative responses between the two treatment arms.

#### **10.7.2.3. Overall Survival**

Overall survival is defined as the time from date of randomization until date of death due to any cause. Subjects who are known to be alive or whose survival status is unknown will be censored at the date last known to be alive. The analysis of the secondary endpoint OS will be performed at the time of PFS primary analysis. Similar to PFS, OS will be analyzed using log-rank test and Cox proportional hazards model.

- The null hypothesis is HR (hazard ratio for Arm A vs Arm B)  $\geq 1$  and the alternative hypothesis is HR  $< 1$ .
- With an alternative HR of 0.39, 33 deaths at the analysis for primary endpoint provides approximately 69% power, based on a log-rank test, a 1-sided overall significance level of 0.025 and 229 randomized subjects.

EAST 6.4 was used for the power calculation and the calculation of the alternative HR of 0.39 is based on the estimated 36-months OS rate of 76% for Arm B (based on the 36-month landmark survival rate of obinutuzumab + chlorambucil arm from Figure 1 of Gazyva® Prescribing Information and the estimated 36-months OS rate of 90% for Arm A (estimated from 30-month landmark OS rate in ibrutinib arm from the Sponsor's Study PCYC-1115-CA).

As an example, Table 7 provides estimates of the events and power.

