## 10.3. Sample Size Considerations

The sample size is calculated based on the assumptions:

- Randomization ratio of 1:1
- Median PFS of 27 months for Arm B (chlorambucil in combination with obinutuzumab)
- Target hazard ratio of 0.55, which corresponds to median PFS of 49.1 months for Arm A (ibrutinib combined with obinutuzumab).
- No interim analysis will be performed.

Assuming an enrollment rate of 18 subjects per month, approximately 212 eligible subjects will be enrolled to observe 94 PFS events in approximately 36 months from the first subject

randomized. On this basis, the study has at least an 80% power to achieve a statistical significance level of 5% (2-sided) under exponential distribution for PFS.

This study is powered based on the primary endpoint PFS. The primary analysis of PFS will be performed when 94 confirmed progression/death events have occurred. The analysis of the secondary endpoint OS will be performed at the time of PFS primary analysis.

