1.4. Sample Size Determination

This study was powered for testing the primary hypothesis of this study.

The sample size is calculated based on the assumptions:

- Randomization ratio of 1:1
- Median PFS of 27 months for Arm B (chlorambucil in combination with obinutuzumab)
- Target hazard ratio of 0.55, which corresponds to median PFS of 49.1 months for Arm A (ibrutinib combined with obinutuzumab).

On this basis, 94 PFS events provide 80% power to achieve a statistical significance level of 5% (2-sided) under exponential distribution. With an estimated accrual rate of 18 subjects per month, approximately 212 eligible subjects were to be enrolled to observe 94 PFS events in about 36 months from the first subject randomized.

The sample size and power calculations were calculated using the software package, East (Cytel Software Corp, Cambridge, MA) version 6.3.

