1.5.2. Primary Analysis

The primary analysis of PFS will be performed after approximately 94 confirmed progression/death events have occurred. The analysis of the secondary endpoints including OS will be performed at the time of PFS primary analysis.

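### Does it matter that the overall survival power statement assumes 229 subjects and 33 deaths when the design plans about 212 subjects and a cut at 94 PFS events?

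*Protocol*

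**What the plan says.** Protocol 10.7.2.3 gives the only OS power statement in either document. For a hazard ratio of 0.39, "33 deaths at the analysis for primary endpoint provides approximately 69% power, based on a log-rank test", with "a 1-sided overall significance level of 0.025 and 229 randomized subjects". The hazard ratio comes from 36-month survival rates of 76% in Arm B and 90% in Arm A (0.899 in Table 7). The software is named ("EAST 6.4 was used for the power calculation") but not the variance option. Table 7 is offered as an example: six scenarios, with 31 to 37 deaths and power from 45% to 78%.

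The design sections use a different sample size. Protocol 10.3: "approximately 212 eligible subjects will be enrolled to observe 94 PFS events in approximately 36 months". SAP 1.4: "approximately 212 eligible subjects were to be enrolled to observe 94 PFS events in about 36 months". Both documents trigger the main analysis by PFS events: "The primary analysis of PFS will be performed when 94 confirmed progression/death events have occurred" (Protocol 10.3) and "The primary analysis of PFS will be performed after approximately 94 confirmed progression/death events have occurred" (SAP 1.5.2). OS is read at the same moment: "The analysis of the secondary endpoint OS will be performed at the time of PFS primary analysis".

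**The concern.** The OS paragraph uses a sample size that appears nowhere else, and a death count that does not follow from the design inputs if nobody drops out. With 229 subjects accrued at 18 per month, the 94th PFS event should come before 36 months, and with 212 subjects fewer deaths should have occurred by then. In either case about two deaths fewer than printed are expected.

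The power figure also looks odd. The usual Schoenfeld formula gives 77% at 33 deaths and a hazard ratio of 0.39, not 69%, and the text does not say which variance was used.

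OS is tested formally in the SAP 1.6 hierarchy. If the result is not significant, readers will use this paragraph to judge how informative it was. A materially wrong power figure would mislead them.

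**Working it through.** **Inputs.** Accrual of 18 per month, 1:1, median PFS 27 months in Arm B and hazard ratio 0.55 (Protocol 10.3). OS rates at 36 months of 0.899 and 0.76, hazard ratio 0.39 and one-sided alpha 0.025 (Protocol 10.7.2.3 and Table 7). My assumptions: uniform accrual, exponential OS and, at first, no dropout. The documents give no dropout rate.

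**Hazards per month.** PFS: Arm B ln 2/27 = 0.02567; Arm A 0.55 × 0.02567 = 0.01412. OS: Arm B −ln(0.76)/36 = 0.00762; Arm A −ln(0.899)/36 = 0.00296.

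**Expected events** at month T with accrual time R = N/18, summed over arms: (N/2) × [1 − (e^(−λ(T−R)) − e^(−λT))/(λR)].

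| | 212 subjects | 229 subjects |
|---|---|---|
| PFS events at 36 months | 93.5 | 99.8 |
| Time of 94th PFS event (months) | 36.2 | 33.7 |
| Deaths at 36 months | 30.7 | 32.7 |
| Deaths at 94th PFS event | 30.9 | 30.4 |

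The PFS plan reproduces with 212 subjects. All six Table 7 death counts (35, 37, 33, 35, 31, 33) reproduce with 229 subjects at 36 months: 34.7, 36.5, 32.7, 34.5, 30.8, 32.6. They also reproduce with 212 subjects at 38.5 months: 35.0, 36.9, 33.0, 34.9, 31.1, 32.9. The table therefore does not identify a single cut.

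**Reproducing 69%.** Use the variance under the alternative, Φ(|ln HR|/√(1/dA + 1/dB) − 1.96). Splitting 33 deaths as the OS rates imply gives dA = 9.68 and dB = 23.32, so 0.9416/√(0.1033 + 0.0429) = 2.463, and Φ(0.503) = 69.3%. The same formula gives 78.3, 67.5, 69.3, 56.6, 58.4 and 44.4% for the six rows, against 78, 68, 69, 57, 59 and 45% printed. The method is inferred from this match. Schoenfeld, Φ(√33/2 × 0.9416 − 1.96), gives 77.2%. Simulating the log-rank test at exactly 33 deaths gives 75 to 76%. The printed method is thus a standard, conservative approximation and not a slip.

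**Power at the planned cut** (base case, no dropout):

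- Apparent protocol method with 212 subjects: dA = 9.09, dB = 21.85, giving 66.5%.
- Simulated log-rank test with the number of deaths left random: 71 to 72% (212 subjects, 36.2 months) and 70 to 71% (229 subjects, 33.7 months).
- Simulation for all six rows with 212 subjects: 81, 68, 71, 56, 60, 44%, against 78, 68, 69, 57, 59, 45% printed. The largest gap is 3 points, and four rows agree within 1.

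The two departures offset each other: the death count is slightly high, and the formula is slightly conservative.

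**Dropout.** Protocol 10.7.1 censors PFS at the last adequate disease assessment, while 10.7.2.3 censors OS at the date last known alive, so PFS can lose more follow-up than OS. Let PFS-only dropout have monthly hazard μ = −ln(1 − annual rate)/12. Expected PFS events then use λ + μ in place of λ, multiplied by λ/(λ + μ); OS is left complete.

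- 229 subjects at 6% per year: 94th PFS event at 36.4 months, 33.1 deaths.
- 229 subjects at 5% per year: 35.9 months, 32.6 deaths.
- 212 subjects at 4% per year: 38.4 months, 32.9 deaths.

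The 6% case with 229 subjects and the 4% case with 212 subjects each round to all six Table 7 counts.

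**The case for a change.** The best case for a change is that one paragraph should describe one analysis, and this one does not say which. If 229 is actual or updated enrolment, the protocol could say so. Even then, without dropout, 229 subjects reach 94 PFS events at 33.7 months with about 30 deaths. When dropout of 0 to 5% per year is applied to PFS and OS alike and accrual varies from 9 to 24 per month, deaths at the trigger stay between 30.3 and 31.5. The unnamed variance option moves the closed-form figure by about 8 points (69% against 77%), more than the sample-size mismatch does. A sentence that the figure is for the OS test alone would also help, since primary PFS and four secondary endpoints come before OS in the hierarchy.

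Part of this stands: 229 is unexplained, and so are the cut and any dropout assumption behind 33 deaths. The rest carries little weight. Two deaths on about 31 is roughly 0.4 of the standard deviation of the death count (about 5.1). Differential loss of PFS follow-up, which the two censoring rules allow, can close the gap. The variance option is a software detail, and the one apparently chosen does not overstate power for the test named. Protocol 10.3 already says that the study is powered on PFS, and SAP 1.6 already sets the testing order.

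**Conclusion.** The inconsistency is real but clerical. The OS paragraph uses 229 subjects where the design says about 212, and about two deaths more than expected at the 94-event cut if there is no dropout. The printed power of approximately 69% lies between the 67% given by the protocol's apparent method and the 70 to 72% from log-rank simulation at the planned cut, so readers are not misled about how much the OS test can show. The figures rest on uniform accrual at 18 per month, exponential survival at the stated rates and no dropout. The reconciliation of 33 deaths with 94 PFS events rests on an assumed PFS-only loss of 4 to 6% per year, and nothing shows that the sponsor used it.

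Sample size, alpha, the 94-event trigger, the OS test and its place in the hierarchy are all set elsewhere and are unaffected. An analyst following the plan would do the same analysis at the same time and reach the same conclusion. A note on where 229 comes from would be a courtesy to readers; the plan does not need it.

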**Table 7: The Predicted HR and Total Expected Events for OS**

36-month OS Rate Ibrutinib + Obinutuzumab	36-month OS Rate Chlorambucil + Obinutuzumab	HR	Power	Total Number of Events
0.899	0.74	0.355	78%	35
0.88	0.74	0.425	68%	37
0.899	0.76	0.39	69%	33
0.88	0.76	0.466	57%	35
0.899	0.78	0.431	59%	31
0.88	0.78	0.515	45%	33

#### 10.7.2.4. Hematological Improvement

Hematological improvement will be evaluated in all subjects and in the subset of subjects with cytopenia(s) at baseline (Hgb  $\leq 11$  g/dL, or platelets  $\leq 100,000/\mu\text{L}$ ), improvement is defined as an increase of Hgb levels from baseline by  $\geq 2$  g/dL, or an increase of platelet counts from baseline by  $\geq 50\%$ . Improvement will be assessed in all subjects at Cycle 9 Day 1 response assessment. Sustained hematologic improvement is defined as hematological improvement that sustained continuously for  $\geq 56$  days without blood transfusion or growth factors.

Percentage of subjects with sustained improvement will be compared using  $\chi^2$  test.

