**Secondary Efficacy Analysis:**

- Overall response rate: the chi-square test will be used to compare the two treatment arms.
- Rate of MRD-negative response: the chi-square test will be used to compare the two treatment arms.
- Overall survival: the two treatment arms will be summarized using Kaplan-Meier point estimates
- Hematological improvement: the percentage of subjects with hematological improvement in the two treatment arms will be measured and compared using the chi-square test.
- EQ-5D-5L: the scores for the five categorical dimensions will be used to compute a single utility score ranging representing the general health status of the subject. The change in utility score from baseline will be summarized. Methods will be detailed in SAP. .

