1.2.2. Secondary Endpoints

- PFS by IRC in high risk analysis set
- Rate of sustained hemoglobin improvement
- Rate of MRD-negative response
- ORR by IRC
- OS
- Rate of infusion related reactions
- Rate of sustained platelet improvement
- Rate of clinically meaningful improvement in EQ-5D-5L utility score

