1.6. Testing Procedure and Level of Significance

To preserve the study wise type I error rate of 0.05, the primary and secondary endpoints will be tested based on a serial gatekeeping testing procedure at the two-sided significance level of 0.05 according to the hierarchical order as listed in 1.2.2.

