2. GENERAL ANALYSIS CONSIDERATION

2.1. Analysis Sets

Intent-To-Treat (ITT) population: defined as all subjects who were randomized. Subjects will be grouped according to the treatment assigned at randomization. This population will be the primary population for the analyses of efficacy endpoints, disposition, demographics and baseline characteristics, baseline disease characteristics, subsequent anticancer therapy and patient-reported outcome data.

Safety population: defined as all subjects who received at least 1 dose of any one of the three study drugs (ibrutinib, chlorambucil, or obinutuzumab). Safety data will be analyzed as treated. The Safety Population will be used to summarize the safety (including dosing and concomitant medications) data.

High risk analysis set: defined as randomized subjects with del17p or TP53 mutation or del 11q at baseline per central lab results.

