4. ANALYSIS FOR ENDPOINTS

Analysis of endpoints will be conducted on the ITT population, unless otherwise specified. Table 1 summarizes the efficacy endpoints and analysis methods to be performed.

The following two randomization stratification factors will be used for the stratified analysis/test: ECOG performance status (0, 1 versus 2) and Cytogenetics (del 17p, del 11q without del 17p, others). To reflect the randomization process and maintain the integrity of randomization, all stratified tests will be based on randomization stratification factors as recorded in the IWRS.

For subgroup and exploratory analysis, only the analysis that provide meaningful information will be presented.

Table 1: Definitions and Analyses for Endpoints

Endpoint	Definition	Analysis Method
Primary Endpoint		
PFS assessed by IRC	Time from the date of randomization to the date of IRC-assessed disease progression or date of death from any cause, whichever occurred first, regardless of the use of subsequent antineoplastic therapy prior to documented PD or death.	
Primary Treatment effect of ibrutinib plus obinutuzumab compared to chlorambucil plus obinutuzumab was tested with a log-rank test. The hazard ratio and its 95% CI based on a Cox regression model are calculated. PFS distribution is estimated by Kaplan-Meier method: median PFS and landmark estimates with 2-sided 95% CIs are to be provided for each treatment arm.
 
Sensitivity Analyzing PFS assessed by investigator using the same method as PFS assessed by IRC.
 
Subgroup Hazard ratio and its 95% CI based on unstratified Cox regression model for each subgroup.

Secondary Endpoints		
PFS assessed by IRC in high risk analysis set	Defined the same as the primary endpoint.	Analyzed the same as primary endpoint in high risk analysis set
ORR assessed by IRC	The proportion of subjects achieving a best overall response of CR, CRi, nPR, or PR per IRC assessment at or prior to initiation of subsequent antineoplastic therapy.	Chi-square test.
Overall survival (OS)	Time from the date of randomization to the date of death from any cause. All deaths observed at the time of the analysis will be considered as events. For subjects who were not known to have died at the time of the analysis, OS data will be censored at date last known alive.	Analyzed the same as PFS primary analysis.

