Rate of MRD-negative response	Proportion of subjects who achieved MRD-negative response defined as < 1 CLL cell per 10,000 leukocytes as assessed by flow cytometry of a bone marrow aspirate or peripheral blood sample per central laboratory.	Chi-square test for MRD-negative response rate by bone marrow

- Rate of infusion related reactions will be analyzed using a Chi-square method.
- Rate of sustained platelet improvement will be analyzed using a Chi-square method
- Rate of clinically meaningful improvement in EQ-5D-5L utility score will be analyzed using a Chi-square method

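### Sustained hemoglobin improvement ranks second of eight in the serial gate but is tested by an unadjusted chi-square; stratifying by baseline anemia could add power at almost no cost

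*Protocol*

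**What the plan says.** - **Rank and gate.** SAP 1.2.2 lists "Rate of sustained hemoglobin improvement" second, after PFS in the high risk set. Under SAP 1.6, "the primary and secondary endpoints will be tested based on a serial gatekeeping testing procedure", at two-sided 0.05 and in that order. MRD, ORR, OS, infusion reactions, platelets and EQ-5D-5L follow.
- **Test.** The protocol synopsis says that "the percentage of subjects with hematological improvement in the two treatment arms will be measured and compared using the chi-square test". Protocol 10.7.2.4 says "Percentage of subjects with sustained improvement will be compared using" a chi-square test. Neither names a covariate or stratum. SAP Table 1, as available, has no hemoglobin row, which may be an extraction loss. For the sibling endpoint the SAP says "Rate of sustained platelet improvement will be analyzed using a Chi-square method".
- **Population.** SAP 2.1 says of ITT: "This population will be the primary population for the analyses of efficacy endpoints". SAP 4 adds: "Analysis of endpoints will be conducted on the ITT population, unless otherwise specified". Protocol 10.7.2.4 looks both at all subjects and at those with baseline cytopenia, and does not say which comparison is the formal one.
- **Stratification.** SAP 4 names ECOG status and cytogenetics, and "all stratified tests will be based on randomization stratification factors as recorded in the IWRS". Baseline anemia is not among the factors.
- **Definition.** Protocol 10.7.2.4 requires a hemoglobin rise of at least 2 g/dL, or a platelet rise of at least 50%, held for at least 56 days without transfusion or growth factors. The cytopenia cut-offs (Hgb ≤11 g/dL, platelets ≤100,000/µL) appear there and in Protocol Table 5.

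**The concern.** The endpoint is a change from baseline, so the baseline value is likely to predict it. Anemia is only one of several ways to meet the treatment criteria in Protocol 4.1, so both anemic and non-anemic subjects will be enrolled. A pooled 2×2 chi-square carries the between-stratum variation in its variance; a stratified test removes it.

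The rank makes this worth attention. If hemoglobin misses 0.05, formal testing stops for the six endpoints behind it, OS included. Platelets have the same structure, but they are seventh and only EQ-5D-5L follows.

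**Working it through.** **Plan's own figure.** The documents state no rate, effect or power for this endpoint. The one design figure that can be checked, the 94 PFS events, reproduces with Freedman's formula: (1.960 + 0.842)² × [(1 + 0.55)/(1 − 0.55)]² = 7.85 × 11.86 = 93.1, rounded up to 94.

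**Inputs from the documents.** Planned N 212, allocated 1:1 (106 per arm); two-sided 0.05; chi-square in ITT; Hgb cut-off 11 g/dL. Protocol 10.7.2.3 also uses 229 randomized subjects, so that size was run too.

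**Assumptions (not in the documents).** 30%, 45% or 60% anemic at baseline; control improvement rates as tabulated; odds ratio (OR) 2.0 or 2.5, common to both strata unless stated.

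**One case by hand.** 45% anemic, control 50% (anemic) and 10% (not anemic), OR 2.5.
- Treated rates: 2.5/3.5 = 71.4% and 0.2778/1.2778 = 21.7%. The risk differences are +21.4 and +11.7 points, so they are not equal under a common OR.
- Pooled rates: control 0.45 × 0.50 + 0.55 × 0.10 = 0.280; treated 0.45 × 0.714 + 0.55 × 0.217 = 0.441; difference 0.161.
- Crude variance × 106: 0.280 × 0.720 + 0.441 × 0.559 = 0.448.
- Within-stratum variance × 106: 0.45 × (0.250 + 0.204) + 0.55 × (0.090 + 0.170) = 0.347.
- Ratio: 0.448/0.347 = 1.29, close to the simulated values for these control rates (1.24 to 1.28).
- Chi-square power by normal approximation: standard error 0.0660 under the null and 0.0650 under the alternative, so Φ[(0.161 − 1.96 × 0.0660)/0.0650] ≈ 69%. Simulation gives 69.5%.

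**Simulation.** 200,000 trials per scenario; Pearson chi-square against CMH stratified by baseline anemia, neither with continuity correction. The power columns are for 45% anemic and OR 2.5. The gain column spans 30% to 60% anemic and OR 2.0 to 2.5. The last column is the variance of the crude risk difference over that of the Mantel-Haenszel risk difference.

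| Control rate, anemic / not | Chi-square | CMH | Gain, points | Variance ratio |
|---|---|---|---|---|
| 60% / 5% | 46.1% | 67.1% | +13 to +21 | 1.55–1.68 |
| 50% / 10% | 69.5% | 79.3% | +8 to +10 | 1.24–1.28 |
| 40% / 20% | 86.3% | 87.8% | +1 to +2 | 1.04–1.05 |
| 35% / 35% | 90.3% | 90.5% | +0.2 to +0.4 | 0.99–1.00 |
| 20% / 20% | 84.9% | 84.7% | −0.4 to −0.2 | 0.99–1.00 |
| 10% / 10% | 66.1% | 65.6% | −0.7 to −0.5 | 0.99–1.00 |

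Multiplying the unrounded variance ratios by 212 gives the trial size without stratification that matches 212 with it: about 328–357, 263–271, 221–223, and 211 where anemia is not prognostic.

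**Weakly prognostic.** At 20%/10% the gain is under 1 point.

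**229 subjects** (45% anemic, OR 2.5): 72.7% against 82.2% (50%/10%), 48.8% against 70.5% (60%/5%), 92.5% against 92.6% (35%/35%).

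**Effect confined to anemic subjects** (45% anemic, 50% to 71.4%; 5% in both arms if not anemic): ITT chi-square 33.3%, ITT CMH 48.4%, chi-square in anemic subjects only 57.6%.

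**Type I error** at 45% anemic: chi-square 4.96% to 5.10%, CMH 4.94% to 5.04%.

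**Platelets** (15% and 25% cytopenic, same control rates and ORs): +1 to +19 points if prognostic, −0.4 to +0.4 if not.

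**The case against.** - **Nothing is broken.** The chi-square holds its level, and the SAP limits stratified tests to the IWRS factors in order to mirror the randomization. True. But adjusting for a pre-specified baseline covariate does not weaken randomization; it needs a written exception to that rule.
- **The SAP's hemoglobin test is not visible.** The protocol sentence covers a hemoglobin or platelet rise, and a SAP row may be missing. This stands as a caveat. If a lost row already stratifies by anemia, the point falls away.
- **The size is assumed.** This stands. Large gains need a strongly prognostic baseline, and the common OR credits treatment with benefit in non-anemic subjects too.
- **The loss can exceed 0.7 points.** At a non-prognostic 5%/5% (45% anemic, OR 2.5), power is 43.0% against 41.8%, a loss of 1.2 points. Correct, and still small.
- **An anemic-only test could be better.** If only anemic subjects benefit, it beats CMH by about 9 to 22 points. But its power ignores the other stratum. At 50%/10% it stays at 57.9% when the effect is shared, where CMH reaches 79.3%. It also differs from the protocol's cytopenic subset, which admits subjects on platelets alone. Keeping ITT is reasonable without data to favor the subset.
- **The gate effect is conditional.** Both PFS tests must pass first. Assuming 28 to 47 of the 94 events fall in the high risk set, that test has about 35% to 54% power at HR 0.55 and 68% to 88% at HR 0.4 (Schoenfeld). If the tests are independent and the primary succeeds, a 10-point gain adds 10 × 0.35 to 10 × 0.88, about 3.5 to 8.8 points, to the chance of reaching MRD. The benefit shrinks but does not vanish.
- **Platelets are less clear.** Their criterion is a relative rise, so the argument from an absolute 2 g/dL rise does not carry over directly. This stands, and the rank makes platelets minor.

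**Conclusion.** The point holds as a missed efficiency for the sponsor to consider. Rank, gate, default population and the IWRS rule are as the documents state. The unadjusted hemoglobin test is the protocol's, and its use in the SAP is inferred.

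Stratifying by baseline anemia is worth about 8 to 21 points of power if anemia is strongly prognostic, 1 to 2 at 40%/20%, and under 1 if the relation is weak. If there is no relation it costs at most about 0.7 points in the main scenarios, or 1.2 at very low response rates. These figures depend on assumed prevalence, rates and odds ratios. The asymmetry between possible gain and loss supports the change. Confidence is medium.

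**What to change.** Before database lock, add to SAP section 4:

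1. Sustained hemoglobin improvement: CMH test in ITT, stratified by baseline Hgb ≤11 versus >11 g/dL. Sustained platelet improvement: CMH test in ITT, stratified by baseline platelets ≤100,000 versus >100,000/µL.
2. A stated exception for these two tests to the rule that stratified tests use the IWRS factors.
3. One line confirming that ITT is the gated population and the baseline-cytopenia subset is supportive.
4. The Mantel-Haenszel risk difference with 95% CI as the reported effect, with a variance that does not assume equal differences across strata. Keep the unadjusted chi-square as a sensitivity analysis.
5. A rule for subjects with a missing baseline value.

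The tests for ORR, MRD, infusion reactions and EQ-5D-5L can stay as they are. The cost is a few lines of SAP text and code. Baseline counts are already collected (Protocol 7.1.2.1), so no new data, visits or subjects are needed.
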